### **5.2.7 PK, PD or Biomarker Analyses**

Baseline MTV, end of treatment MTV, and baseline ctDNA will be associated with CR, PR, and ORR by Wilcoxon rank sum tests. Baseline and post treatment mutations detected by NGS will be associated

with CR, PR, and ORR by Fisher's exact tests. MTV (baseline and end of treatment) and mutations (baseline and post treatment) will be associated with EFS, PFS, and OS using Cox regression treating MTV as time-dependent covariate. Baseline ctDNA will be associated with EFS, PFS, and OS by log-rank tests.

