#### 3.1.3 Pharmacodynamic, Pharmacokinetic and Biomarker Parameters

Exploratory correlative studies of tumor tissue, when available, may include characterization of tumor subtypes by NGS, including comparing pre- and post- study treatment biopsies in patients without a clinical response and/or progression of disease. Baseline and end of treatment (EOT) PET scan will be assessed for response by MTV as a correlative biomarker.

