**MTV CORRELATE:****Screening and EOT scans for each patient enrolled will be sent to UM for central review.**

PET/CT scans at enrollment and EOT from mid-skull to upper thighs will be obtained ~90 minutes after injection on Philips Gemini TF PET/CT systems (Philips Medical Systems, Cleveland, Ohio). A clinical imaging protocol will be applied with an injection of approximately 555 +/- 10% MBq FDG after at least 4 hours of fasting and documentation of blood glucose <200 mg/dL. A low-dose, attenuation correction CT scan (120 kV, approximately 100 mA) will be acquired, following by PET emission images. All images will be reviewed on Thinking Systems software. Region of interest will be set by manual adjustment in 3 planes to exclude adjacent physiologic FDG avid structures. SUV max will be defined as the maximum voxel intensity within the volumetric region of interest. A threshold of 41% of the maximum signal intensity will be used to delineate the metabolic tumor volume (MTV) however, other thresholds will be evaluated. Patient MTV represents the sum of every individual lesion MTV. The TLG will be calculated as the product of MTV and the SUV mean using Hermes Hybrid 3D Tumor Finder for MTV software.

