##### Complete Response (CR):

- CR is defined as a complete resolution of all target lesions by CT scans with complete normalization of FDG-PET uptake in all areas (Deauville score of 1–3), and bone marrow biopsy negativity (if it was positive or unknown at baseline). If pretreatment PET scan was negative, lymph nodes that measured  $\geq 15$  mm in the long axis should regress to  $< 10$  mm.
- CR is also defined as achievement of a partial remission by CT scan criteria (reduction in sum of longest diameters by CT imaging by  $>30\%$ ) with normalization (Deauville score 1–3) of FDG-PET activity in FDG-avid lymphoma (Table 1). Because many novel targeted agents may alter glucose uptake and/or metabolism, normalizing of FDG-PET imaging alone is not sufficient by itself to determine CR status unless accompanied with a significant ( $>30\%$ ) decrease in the sum of diameters. Accordingly, a reduction in the sum of diameters by  $\leq 30\%$  with normalization of FDG-PET uptake should not be considered a CR unless documented by a negative tissue biopsy.
- Deauville Criteria 5-point scale:
  1. No uptake.
  2. Uptake  $\leq$  mediastinum.
  3. Uptake  $>$  mediastinum but  $\leq$  liver.
  4. Uptake moderately more than liver uptake, at any site.
  5. Markedly increased uptake at any site and new sites of disease.
- In cases where pretreatment baseline tumor burden is low, with only a few lesions measuring around 2 cm in longest diameter, treatment effect may shrink the long axis of a target lymph node to a normal values of  $<10$  mm.

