f	Samples can be taken on the day of or day prior to dosing. The results do not need to be available before the dose of study drug is given.
g	Computed tomography and PET scans obtained for standard subject evaluations before signing ICF can be used for screening, but should not be older than 28 days prior to enrollment.
h	Computed tomography scan and PET scans will be performed at screening and at the end of Cycle 3. CT scan will occur Day 15-21 of Cycle 2 to demonstrate lack of progression of disease (PD)  . If PD, patient will be removed from study. Positron emission tomography scans must be done between Days 15 to 21 of Cycle 3.
i	Computed tomography and PET scans are required at early withdrawal. Computed tomography and PET scans performed after Cycle 3 are considered the End-of-Treatment disease efficacy assessment (or earlier if $< 3$ cycles administered as per investigator discretion). If early withdrawal prior to the end of Cycle 3, CT and PET scans are to be repeated.
j	Morphological and IHC examination of the bone marrow is required and should be performed within 28 days prior to the first dose of study drug. In subjects with bone marrow involvement prior to treatment, bone marrow biopsy must be repeated once during the study for confirmation of CR (preferentially within 30 days of initial documentation of CR). Bone marrow obtained for standard subject evaluations before signing ICF can be used for screening, but should not be older than 28 days prior to treatment.
k	If this visit occurs within 7 days of Cycle 1 Day 1. It may be used for the screening and Cycle 1 Day 1 treatment evaluations.
l	A directed physical exam, chemistry (potassium) and urinalysis assessments will be performed every day while participants are receiving R-ICE treatment.
m	RNB for patients with evaluable clonotype determined on pretreatment tumor specimen. Required ctDNA assessment time points: pre-treatment, and at EOT.
n	Follow-up every 12 weeks for 52 weeks after EOT visit, until removal from study, or until death. SAEs considered related to study drug should be documented
o	A patient diary will be provided to participants and study team members will advise participants on how to record information in the diary.

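### Section 5.2.7 tests end-of-treatment MTV against a CR read from the same PET, and models post-treatment mutations without naming their source or handling when they become known (exploratory analyses only)

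*Combined protocol and SAP*

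**What the plan says.** **MTV.** Section 5.2.7 reads: "Baseline MTV, end of treatment MTV, and baseline ctDNA will be associated with CR, PR, and ORR by Wilcoxon rank sum tests". Section 4.1.15 (MTV correlate) says "PET/CT scans at enrollment and EOT from mid-skull to upper thighs will be obtained". Appendix 1, footnote i, says "Computed tomography and PET scans performed after Cycle 3 are considered the End-of-Treatment disease efficacy assessment". Section 4.1.16 makes CR depend on "complete normalization of FDG-PET uptake in all areas" (Deauville 1–3), together with CT criteria and, where applicable, a negative marrow. Its second route to CR accepts CT shrinkage above 30% with a normalised PET. Section 3.1.3 declares the purpose: "Baseline and end of treatment (EOT) PET scan will be assessed for response by MTV as a correlative biomarker".

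**Mutations.** Section 5.2.7 continues: "Baseline and post treatment mutations detected by NGS will be associated" with CR, PR and ORR by Fisher's exact test, and MTV and "mutations (baseline and post treatment) will be associated with EFS, PFS, and OS using Cox regression treating MTV as time-dependent covariate". Section 5.2.6 starts PFS, EFS and OS at first dose. Section 5.2.7 does not name the source of the post-treatment mutations. Section 2.3 refers to sequencing of tumor. The synopsis and Section 3.1.3 say the correlative work may compare biopsies before and after treatment in patients without response and/or with progression. The Appendix 1 schedule lists no post-treatment tumor biopsy. Cell-free DNA is also collected before treatment and at end of treatment (Section 4.1.15; Appendix 5), for tracking alterations already found before treatment.

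**Separate item, Appendix 5.** The shipping section has sites outside Sylvester send CPT tubes by overnight courier. The CPT processing section expects cells to degrade after more than four hours in the tube.

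**The concern.** A test of end-of-treatment MTV against CR compares two reads of one image. A small p-value is close to guaranteed by the response definition, yet it could be reported as biomarker evidence.

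Post-treatment mutations raise a different problem. If they come from biopsies of patients who failed treatment, there are few or no responders to compare with, and the survival sample is chosen on its outcome. If they come from end-of-treatment plasma, the sample of a patient who stops for progression is drawn after the event it is meant to predict. The plan makes MTV time-dependent but says nothing equivalent for mutations, so the natural reading is a fixed covariate from first dose. Results would then partly reflect who was sampled and when. No trial decision rests on these analyses.

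**Working it through.** Section 5.2.7 gives no power, significance level or effect size, so there is no stated figure to reproduce. From Section 5.1: 46 patients in all, 20 in stage 1, at least 7/20 CR to continue, at least 18/46 CR for success, and a 50% target (23/46). From Section 1.2.3: 12-month PFS of 0.62 with ibrutinib + R-ICE, borrowed here as an assumption. All other inputs are assumptions.

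**A. End-of-treatment MTV against CR**

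*Limiting case.* Every CR has MTV 0 and every non-CR has more. For 18 CR and 28 non-CR, the Mann-Whitney mean is 18×28/2 = 252. The tie-corrected variance is (504/12)×[47 − (18³−18)/(46×45)] = 42×(47 − 2.81) = 1856, so the SD is 43.1. With continuity correction z = 251.5/43.1 = 5.84 and p = 5.3×10⁻⁹. For 23 against 23, p = 5.7×10⁻¹⁰. These are upper bounds on the circularity, because CR also needs CT and sometimes marrow criteria.

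*Relaxed case.* Let d be the share of CR patients with measurable MTV, and equally the share of non-CR patients with none. Positive MTV has the same lognormal distribution in both groups. Share of tests with p<0.05:

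| d | 7 of 20 CR | 18 of 46 CR | 23 of 46 CR |
|---|---|---|---|
| 10% | 93% | 100% | 100% |
| 20% | 66% | 97% | 98% |
| 30% | 31% | 70% | 73% |
| 40% | 11% | 23% | 24% |
| 50% (no relation) | 4% | 5% | 5% |

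These are not error rates. They show that the result follows the agreement between two reads of one scan. PR in Section 4.1.16 rests mainly on CT, so the overlap is weaker for PR and ORR.

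**B. Post-treatment tissue mutations against response (Fisher)**

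Suppose 10 non-responders are sampled. The smallest two-sided p over all tables is:

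- 0 responders: 1.00 (no comparison exists)
- 1 responder: 1/11 = 0.09
- 2 responders: 1/C(12,2) = 1/66 = 0.015

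**C. Post-treatment tissue mutations against PFS**

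Assume exponential PFS and 14 months of follow-up. Expected events are 46×(1 − 0.62^(14/12)) = 46×0.43 ≈ 20. The mutation has prevalence 20% or 40% and no effect, and 30–80% of progressors are biopsied (about 6–16 patients). Rejection at nominal 5%, 4,000 simulated trials per scenario:

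- unsequenced patients left out: about 7–10%
- unsequenced patients coded mutation-absent: 34–97%

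If non-responders are also eligible and 20% of PFS events are deaths without biopsy, the ranges are 6–9% (about 6–20 patients) and 19–73%.

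**D. End-of-treatment plasma variants against PFS**

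The PET falls on Days 15–21 of Cycle 3, that is day 42+15 = 57 to 42+21 = 63 without delays; day 63 is taken as end of treatment. At a constant hazard, 1 − 0.62^(63/365.25) = 7.9% of patients, or 3.6 of 46, have a PFS event by then. The phase I summary in Section 1.2.3 states 1 of 21 patients (5%) removed for rapid progression. Counting the 20 − 18 = 2 evaluable non-responders as well gives at most 3/21 = 14%.

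- Detection assumed 60% or 90% in early progressors and 30% in others, 10–20% progressing early: 10–62% rejection from first dose
- Same detection, 5–8% progressing early: about 7–18%
- Equal detection in everyone: about 5–6%
- Models started at the draw among event-free patients (10–20% progressing early): 4–6%, on about 22–37 patients with 6–14 later events

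**The case against.** Section 3.1.3 openly plans to assess response by MTV, and Section 4.1.15 will try other MTV thresholds. CR has CT and marrow components, and the table in A runs from 4% to 100% on an assumed discordance. This stands in part: describing MTV by response is legitimate, and the table does not measure the overlap. The shared scan and the Deauville requirement are nevertheless written into the plan, so a significance test against CR adds little.

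For the mutations, three stronger readings are tempting, and the documents do not support them.

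- *The source is stated nowhere.* The synopsis and Sections 2.3 and 3.1.3 point to tumor tissue. What is missing is a statement in 5.2.7 of which source it uses.
- *The survival tests reject falsely in 34–97% of cases.* That requires coding unsequenced patients as mutation-absent, which the plan nowhere says. With those patients left out, the inflation is modest.
- *Plasma variants reject falsely in 10–62% of cases.* That requires higher detection in early progressors and 10–20% early progression, both assumed. With equal detection there is essentially no inflation. Section 5.2.7 also treats ctDNA as a separate, baseline-only variable, so plasma is the less likely reading. A sample drawn after progression still precedes death, so the argument does not carry over to OS.

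Fixed coding is itself inferred from silence. Dropping patients with an event before the measurement, under independence, gives a median hazard ratio of 1.00–1.02 and about 5% rejection. Fixed coding alone is therefore not the fault; selective sampling and the unstated handling of unmeasured patients are.

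**Conclusion.** The point holds as a minor correction to exploratory analyses. The test of end-of-treatment MTV against CR is largely, though not wholly, circular. On the tissue reading, which the documents favour, the Fisher comparison has few or no responders and the survival sample is selected on outcome. The Fisher minimum p-values are exact for the assumed counts. The 7–10% rests on exponential PFS, a borrowed 12-month rate and assumed prevalence and sampling. Anything much larger depends on rules or detection rates that the documents do not give.

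A reader might infer that the primary CR result is compromised. It is not: none of these analyses enters the two-stage rule in Section 5.1. The conflict in Appendix 5 is real, but it concerns sample handling and adds no weight to the point about 5.2.7.

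**What to change.** In Section 5.2.7:

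1. Replace the test of end-of-treatment MTV against CR with a descriptive summary of end-of-treatment MTV by response category. This still serves Section 3.1.3. Keep baseline MTV against response.
2. State the source of post-treatment mutations.
   - *If tissue:* report them descriptively as paired pre/post changes, with the number sampled out of those eligible, and never code unsequenced patients as negative.
   - *If end-of-treatment plasma:* start the EFS and PFS models at the draw among patients event-free then, and the OS model at the draw among patients alive then.
3. Keep baseline mutations as planned.

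The cost is a few sentences, with no new samples or visits. On the plasma reading, patients with an earlier event leave those models. For PFS this is about 46×0.10 ≈ 5 to 46×0.20 ≈ 9 of 46 patients at an assumed 10–20%, or about 4 at the 7.9% computed above.

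Separately, reconcile the shipping and CPT processing instructions in Appendix 5. Until then, report buffy-coat BCR/MRD results by time to processing, which removes no samples. A strict time limit could remove every such sample from the two additional centers.

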### **2.3 EXPLORATORY OBJECTIVE(S)**

Correlate efficacy endpoints (ORR, PFS, OS) with: baseline metabolic tumor volume (MTV), circulating cell-free tumor DNA (ctDNA), and the results of next-generation sequencing (NGS) of tumor. NGS in diagnostic biopsy if available.

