##### Partial Response (PR):

- PR is defined as a reduction of the sum of longest diameters of target lesions by  $\geq 30\%$ , but without meeting the definition of CR. If one or more target lesions grew in size but the sum of the diameters remains  $\leq 30\%$  of the baseline measurement, and no new lesions appear, the response should be designated PR.

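### Objective 2.3 asks how baseline MTV relates to PFS and OS, but the only MTV survival model specified in Section 5.2.7 is time-dependent and does not estimate that association

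*Combined protocol and SAP*

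**What the plan says.** Section 2.3 sets the exploratory aim: "Correlate efficacy endpoints (ORR, PFS, OS) with: baseline metabolic tumor volume (MTV), circulating cell-free tumor DNA (ctDNA), and the results of next-generation sequencing". The MTV it names is the baseline value, and the endpoints are ORR, PFS and OS.

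Section 5.2.7 then gives the methods:

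- **MTV and ctDNA against response:** "Baseline MTV, end of treatment MTV, and baseline ctDNA will be associated with CR, PR, and ORR by Wilcoxon rank sum tests".
- **Mutations against response:** tested "with CR, PR, and ORR by Fisher's exact tests".
- **MTV (baseline and EOT) and mutations against survival:** "associated with EFS, PFS, and OS using Cox regression treating MTV as time-dependent covariate".
- **ctDNA against survival:** "Baseline ctDNA will be associated with EFS, PFS, and OS by log-rank tests".

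No Cox model with baseline MTV held fixed is described. The form of the time-dependent model is not given, and neither is the comparison group for the PR tests. Section 4.1.16 defines PR as a reduction of at least 30% in the sum of longest diameters, "but without meeting the definition of CR", so the two categories are mutually exclusive.

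**The concern.** A time-dependent covariate carries the most recent value. With one value at baseline and one at EOT, each patient contributes baseline MTV only until the EOT scan. After that the model compares patients on residual MTV. That answers a legitimate question about current disease burden, but objective 2.3 asks a different one: does the burden measured before treatment predict PFS and OS? If most events follow the EOT scan, a real baseline effect is diluted. A positive coefficient could also come entirely from residual disease and be reported as a baseline effect.

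The PR test raises a separate, smaller matter. Response is ordered, and PR sits in the middle. Comparing PR with everyone else sets the middle category against the best and the worst together. A marker that worsens steadily from CR through PR to non-response will then show almost nothing, and the null result could be misread as evidence against the marker.

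**Working it through.** Section 5.2.7 states no sample size, power or alpha, so there is no figure in the plan to reproduce. Two-sided 0.05 is assumed throughout.

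**1. When the MTV value switches.** Appendix 1 places the PET on Days 15-21 of Cycle 3. With 21-day cycles this is day 2×21+15 = 57 to day 3×21 = 63, or weeks 8-9. Section 3.8 allows a delay of up to 7 days per new cycle. Two delays take day 63 to day 77, week 11. Weeks 9 and 12 are used as bounds. Section 4.4 gives 52 weeks of follow-up after EOT, so observation runs to about week 61.

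**2. Share of events after the switch.** Under a constant hazard with one-year survival S, switch at week t and follow-up to week f:

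share after = 1 − [1 − S^(t/52)] / [1 − S^(f/52)]

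Section 1.2.3 gives one-year EFS 0.51 and PFS 0.62 for the phase I study of ibrutinib with R-ICE.

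- S = 0.51, t = 9, f = 61: 1 − 0.110/0.546 = 0.80
- S = 0.51, t = 12, f = 61: 1 − 0.144/0.546 = 0.74
- S = 0.50, t = 10, f = 62: 1 − 0.125/0.562 = 0.78
- S = 0.62, t = 10, f = 62: 1 − 0.0878/0.434 = 0.80

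**3. What the planned coefficient estimates.** The model is λ(t) = λ0(t)·exp{β·Z(t)}, with Z(t) equal to baseline MTV before the EOT scan and EOT MTV after it. Data were simulated for 46 patients (the maximum in Section 5.1) with a hazard that depends only on baseline MTV. The effect sizes and the baseline-EOT correlation are assumptions.

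True hazard ratio 1.8 per SD, correlation 0 to 0.6:

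- Planned time-dependent term: median hazard ratio 1.12-1.46, power 7-44%.
- Baseline MTV fixed: median hazard ratio 1.79-1.85, power 70-83%.
- A second run with the switch at week 9 or 12 gave the planned term 8-14% power at correlation 0, and 17-50% (hazard ratio 1.28-1.51) at 0.3-0.6.

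True hazard ratio 2.0 per SD, switch at week 10, follow-up to week 62, one-year PFS 0.50 or 0.62, 500 runs each:

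| Correlation | Planned term: HR | Planned term: power | Fixed baseline: HR | Fixed baseline: power |
|---|---|---|---|---|
| 0 | 1.19-1.20 | 12-16% | 2.00-2.04 | 84-91% |
| 0.3 | 1.37 | 30-34% | 2.03-2.05 | 86-94% |
| 0.6 | 1.57-1.58 | 52-60% | 2.01 | 84-91% |

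When the hazard depends only on EOT MTV (hazard ratio 2.0), the same planned term gives 1.67-1.76. The coefficient therefore cannot show which of the two values carries the association.

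**4. The PR test.** Assume 46 patients with CR/PR/other at 50/20/30%, that is 23, 9 and 14, and a normal marker shifted 0.5 SD per category. The chance that a patient one category better has the higher marker is Φ(0.5/√2) = 0.638; for two categories it is Φ(1.0/√2) = 0.760. The Wilcoxon test compares the following probabilities with 0.5:

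- PR against the rest: (23×0.362 + 14×0.638)/37 = 0.47
- CR against the rest: (9×0.638 + 14×0.760)/23 = 0.71
- ORR (CR or PR) against the rest: (23×0.760 + 9×0.638)/32 = 0.73

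Simulated power in this setting (4,000 runs) is 5% for PR, 70% for CR, 69% for ORR and 79% for one ordered test over the three categories. Across four other mixes (CR 29-50%, PR 25-34%), PR against the rest has 4-9% power, against 58-67% for CR and 54-67% for ORR. At 1.0 SD per category the PR test has 1-18%, and CR and ORR have at least 98%. If PR were meant to be compared with non-responders only, power would be 18-26% at 0.5 SD.

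**The case against.** A reader might infer that Section 5.2.7 cannot answer objective 2.3 at all. The documents do not support that. The response sentence tests baseline MTV and baseline ctDNA directly against ORR, the one response endpoint that 2.3 names, and mutations are tested against ORR as well. Baseline ctDNA has its own log-rank tests, and mutations are not called time-dependent. PR alone is not an endpoint in 2.3, so a weak PR test is an uninformative extra that removes nothing from the objective.

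It is also tempting to say that the baseline effect is erased. That is close to true only at zero correlation between baseline and EOT MTV. At 0.6 the effect is attenuated and still partly visible. Low correlation is plausible, because CR requires PET normalization and the design targets 50% CR, which would leave EOT MTV near zero in many patients whatever their baseline. The documents give no value, however, so only a range can be quoted.

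Two readings are inferred. The text lists both MTV values without giving the model form, and it does not state the PR comparator. The readings used here are the usual ones. If others were intended, the plan needs to say so.

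Finally, these analyses are exploratory, in at most 46 patients, and no stopping rule or primary or secondary conclusion rests on them. That limits the weight of the point. It does not change the mismatch between the objective and the stated method.

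**Conclusion.** The concern holds for one part of objective 2.3: baseline MTV against PFS and OS. On the usual meaning of a time-dependent covariate, the specified model estimates a mixture dominated by the post-EOT period. With an assumed baseline-only hazard ratio of 1.8 per SD, it understates the effect (median about 1.1-1.5) and loses most of the power that a fixed term would have. These sizes rest on a constant hazard, survival figures from a study of a different BTK inhibitor, and assumed effect sizes and correlations. The direction of the problem depends only on the EOT value replacing the baseline value.

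The PR yes/no test is a secondary defect. On its natural reading it has close to null power for a marker that tracks response in order.

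**What to change.** In Section 5.2.7:

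1. Fit baseline MTV as a fixed covariate from first dose in its own Cox model for each of EFS, PFS and OS. Name this as the analysis that addresses objective 2.3.
2. Analyse EOT MTV separately, for example with a landmark at EOT: time counted from the EOT scan, among patients still event-free and under follow-up then. If the time-dependent model is kept, label it as an analysis of current MTV and write out its form.
3. Drop the PR yes/no Wilcoxon and Fisher tests. Keep ORR, because 2.3 names it, and CR. One ordered-response test per marker may be added, for example Jonckheere-Terpstra for MTV and ctDNA and Cochran-Armitage for mutations. If a PR contrast is wanted, state its comparison group.

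The cost is SAP wording only: no new data, scans or patients. It should be settled before outcomes are examined, because choosing the MTV model or the PR comparator afterwards would be data-driven.

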#### **4.1.15 Pharmacodynamics/Pharmacokinetics and Biomarker Studies**

##### **TUMOR BIOPSY and ctDNA:**

Identification of Tumor-Specific BCR Clonotype from pre-treatment tumor biopsy and tracking of MRD:

The specimens collected at pre-treatment (typically, lymph node biopsy) archival tissue will be shipped to Foundation One Heme. Details regarding recommended specimens are outlined in the Manual of Procedures

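### Section 5.2.7 tests post-treatment NGS mutations against response, but the post-treatment tumor tissue described comes from non-responders and progressors, so availability of the result depends on the outcome

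*Combined protocol and SAP*

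**What the plan says.** - **Analysis.** Section 5.2.7: "Baseline and post treatment mutations detected by NGS will be associated" "with CR, PR, and ORR by Fisher's exact tests". The same section relates baseline and post-treatment mutations to EFS, PFS and OS by Cox regression. MTV is the only covariate it names as time-dependent. No significance level or multiplicity rule is given for these tests.
- **Post-treatment tissue.** Section 3.1.3: "Exploratory correlative studies of tumor tissue, when available, may include characterization of tumor subtypes by NGS", and among these studies it names "comparing pre- and post- study treatment biopsies in patients without a clinical response and/or progression of disease". The synopsis carries the same description.
- **Specimen with a stated collection.** Section 4.1.15: "The specimens collected at pre-treatment (typically, lymph node biopsy) archival tissue will be shipped to Foundation One Heme". No matching sentence covers post-treatment tumor tissue.
- **Meaning of NGS.** Section 2.3 lists ctDNA as one correlate "and the results of next-generation sequencing (NGS) of tumor" as another, so the two are separate sources.
- **Blood.** Appendix 1, footnote m: "Required ctDNA assessment time points: pre-treatment, and at EOT". This does not depend on response, but it applies to patients with an evaluable clonotype. Section 5.2.7 uses only the baseline ctDNA value.

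**The concern.** A test of association between a marker and response needs the marker in both responders and non-responders, sampled in a way that does not depend on response. Here the described sampling of post-treatment tumor is set by the outcome. Response is fixed at the end of cycle 3 (Section 5.2.1). A patient with lasting CR or PR then has no planned tumor specimen, while a non-responder or a patient who progresses may have one.

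What is at stake is an exploratory result that either carries no information or is reported as a correlate of response when it reflects who was biopsied. The baseline-mutation tests in the same sentence use pre-treatment tissue and do not have this problem.

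**Working it through.** The plan gives no sample size, power or alpha for the biomarker tests, so there is no figure to reproduce. The two situations that the plan can produce are worked through below.

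**Inputs.** N = 46 (Section 5.1). ORR 63% (CORAL, Section 1.1) and 90% (phase I ibrutinib + R-ICE, Section 1.2.3). One-year PFS 0.62, 95% CI 0.43 to 0.9 (Section 1.2.3). Applying these rates to this trial is an assumption. So is a two-sided 0.05 level.

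**Situation 1: no biopsied responder, or one.** The Fisher table with rows responder (0, 0) and non-responder (a, b) has an empty row. The odds ratio is undefined and p = 1 for every a and b. With one biopsied responder and m non-responders, the most extreme table has probability 1/(m + 1):
- ORR 63%: m = 46 × 0.37 ≈ 17, so the smallest p is 1/18 = 0.056.
- ORR 90%: m = 46 × 0.10 ≈ 5, so the smallest p is 1/6 = 0.167.

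Neither can reach 0.05.

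**Situation 2: responders who relapse are biopsied.** Suppose every PFS event is a biopsied progression and all non-responders are among the first-year events. Then biopsied relapsed responders ≈ 46 × (1 − PFS) − non-responders, with a floor at 0.

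| One-year PFS | Events | ORR 63% (17 non-responders) | ORR 90% (5 non-responders) |
|---|---|---|---|
| 0.90 | 46 × 0.10 ≈ 5 | 0 | 0 |
| 0.62 | 46 × 0.38 ≈ 17 | 0 | 12 |
| 0.43 | 46 × 0.57 ≈ 26 | 9 | 21 |

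The range is about 0 to 21. Deaths without biopsy and progressions not biopsied would lower these counts. Non-responders who stay event-free would raise them.

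**Bias in situation 2, on assumed values.** Take a mutation present in 30% of patients and unrelated to response. Let relapse among responders be 50% if mutated and 25% if not. Among relapsed responders its prevalence is

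0.30 × 0.50 / (0.30 × 0.50 + 0.70 × 0.25) = 0.15 / 0.325 = 46%,

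against 30% in non-responders. The table shows a difference by response although none exists. It arises because only relapsing responders were sampled.

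**Power, on assumed values.** With prevalence 50% in 17 non-responders and 10% in responders, sequencing all 29 responders gives Fisher power of about 82%. With 3, 5, 8 or 12 biopsied responders, power is about 5%, 19%, 42% and 57%. These figures ignore the bias above.

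**Cox models.** A mutation read from tissue taken at progression becomes known only when the PFS and EFS event has already happened, so it cannot act as a predictor of that event. For OS, the value exists only in patients who lived to non-response or progression and were biopsied.

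**The case against.** Four points can be made for the plan.

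1. *The wording is permissive.* Section 3.1.3 and the synopsis describe what the studies may cover, subject to availability, and neither says that other patients are excluded. That is right, so a reader who infers a hard restriction to non-responders goes beyond the text. Even so, no section plans post-treatment tumor sequencing in sustained responders, and tissue obtained by chance would still be selected. The Manual of Procedures and the laboratory manual may say more, but they are not part of these documents.

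2. *Responders do have post-treatment tissue.* Appendix 1, footnote j, repeats the marrow biopsy to confirm CR in patients with marrow involvement at baseline, and Section 4.1.16 lets a negative tissue biopsy establish CR. So it would be wrong to infer that no post-treatment biopsy is scheduled for anyone. Neither sample is stated to go for NGS, however, and each is taken to show absence of lymphoma. Nor does the lack of a tumor-biopsy row in Appendix 1 prove much, since pre-treatment tumor tissue has no row either.

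3. *Section 5.2.7 does not name the specimen.* Sequencing of cell-free DNA could supply the mutations. This is possible, but Sections 2.3 and 5.2.7 both treat ctDNA separately, so tumor is the more natural reading. The point stands as a reason to name the specimen and to offer ctDNA as an alternative.

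4. *The analysis is exploratory.* No decision rests on it, and the baseline tests address the diagnostic-biopsy part of the objective. This limits the consequence but does not make the test interpretable.

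**Conclusion.** The stated analysis does not fit the described sampling. Following the plan gives either a degenerate Fisher test (p = 1) or a comparison of relapse tumors with refractory tumors. Neither estimates an association between post-treatment mutations and CR, PR or ORR. The Cox terms for post-treatment mutations share the defect.

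Two stronger readings are not supported. A reader might infer that the comparison must contain essentially no responders. The description also covers progression, which admits initial responders who relapse, from about 0 to 21 of 46 under the assumptions shown, so in some scenarios the fault is selection and not an empty group. A reader might also infer that at least 23 patients in CR would lack tissue. But 46 × 0.5 = 23 is the expected number of CRs at the target rate, and fewer than 23 would occur about 44% of the time.

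The conclusion rests on reading NGS in Section 5.2.7 as tumor NGS and on there being no further collection plan in manuals outside these documents. The primary CR analysis and the baseline-mutation tests are unaffected. The correction is worth making because it needs only wording.

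**What to change.** In Section 5.2.7:

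- Keep the tests of baseline mutations.
- Delete the Fisher tests of post-treatment tumor mutations against CR, PR and ORR, and the post-treatment mutation terms in the Cox models for EFS, PFS and OS.
- Replace them with a descriptive paired comparison of pre- and post-treatment mutations (gained, lost, retained) in biopsied patients, reported separately for non-responders and for responders who later progress, with the number biopsied out of the number eligible in each group.
- State which specimen supplies post-treatment mutations and in which patients.
- If a post-treatment comparison with response is wanted, define it from the end-of-treatment ctDNA (Section 4.1.15; Appendix 1, footnote m), limited to patients with an evaluable clonotype or trackable variants. Note that this assay follows variants found before treatment, so it would not show newly acquired ones.

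The cost is a wording change and fewer exploratory p-values. No new visits or samples are needed, because the end-of-treatment blood is already collected. Using it for a response comparison would add an analysis that Section 5.2.7 does not now contain.
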